### 14.6. Secondary Analysis (For Part 1 and Part 2)

#### Relationship between Comfort Scores and Clinical Measures

Correlation analysis will be conducted between subjective comfort scores (VAS scale) and primary endpoints. Pearson product-moment correlation coefficient will be provided for continuous endpoints and Kendall's tau coefficient will be provided for ordinal endpoints. For each of the primary endpoints, when there is more than one measurement taken for each subject (eye for WBC), the mean will be used in the analysis and a test based on the corresponding correlation coefficient will be conducted separately.

Tests for the relationship between the comfort scores and each of the primary endpoints will be conducted separately using two-sided 95% confidence intervals constructed for the corresponding correlation coefficient. The relationship between comfort scores and a primary

# Clinical Study Protocol

## Johnson & Johnson Vision Care, Inc.

endpoint will be concluded to be significant if 0 does not fall within confidence limits of the corresponding coefficient. The directional statistical relationship will be determined using the upper or lower limit of the 95% confidence interval. Upper limit below zero or lower limit above zero of the 95% confidence will determine negative or positive relationship, respectively, between the clinical measure and the VAS score. Further analysis based on a linear model or a generalized linear model depending on the distribution of the VAS scale may be undertaken if necessary when the relationship between comfort scores and any one of primary endpoints is significant.

### **14.7. Other Hypotheses**

#### **For Part 2:**

The analysis procedure will follow the exact steps for analyzing these hypotheses as described in the primary analysis section for LMS, NIBUT, TMH, TOSM, and WBC.

#### **For Part 1 and 2:**

1. For Part 1 and 2: End of day discomfort will return to pre-lens wear comfort levels following lens removal.

Within each stratum and overall post VAS score for both eyes will be analyzed separately using a linear mixed model by adjusting the baseline VAS score (pre-VAS) as covariate. The model will include subject strata (asymptomatic/symptomatic) as fixed effect. Other characteristics such as, age, gender, and race will be included as fixed covariates when appropriate. Unstructured (UN) and Homogenous Compound symmetry (CS) Covariances will be considered to model the residual errors between the eyes from the same subject (R-side). A two-sided 95% CI for the coefficient of the model intercept will be constructed for the hypothesis given below:

$$\begin{aligned} H_0: \beta_{int} &= 0 \\ H_A: \beta_{int} &\neq 0, \end{aligned}$$

where  $\beta_{int}$  =model intercept. End of day discomfort returned to pre-lens wear comfort will be concluded if the 95% confidence intervals contains 0. Otherwise, statistical difference between end of day comfort and pre-lens comfort will be concluded. The direction will be determined using the upper or lower limit of the 95% confidence interval. Upper limit below zero or lower limit above zero of the 95% confidence will determine negative or positive change, in other words, lower or higher post VAS score compared to pre-VAS score, respectively.

2. There will be a relationship between change in CLDEQ score between Part 1 and Part 2 and change in the five clinical parameters investigated between Part 1 and Part 2.

Correlation analysis will be conducted for the change in CLDEQ score and the change in the five clinical parameters between Part 1 and Part 2. Pearson product-moment correlation coefficient will be provided for continuous endpoints, and Kendall's tau coefficient will be

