# **Clinical Study Protocol**

## **Johnson & Johnson Vision Care, Inc.**

5. Symptomatic subjects will have, on average, statistically significantly, greater density of white blood cells (visualized by confocal microscopy) in both the upper and lower lid margins compared to asymptomatic subjects after 6 hours of lens wear.

For Part 1 and 2:

1. The measured end of day discomfort score, following lens removal, will not be statistically significantly different than the pre-lens wear discomfort score.
2. There will be a statistically significant relationship between change in CLDEQ score between Part 1 and Part 2 and a change in the five clinical parameters investigated between Part 1 and Part 2.
3. There will be a statistically significant relationship between change in CLDEQ score between Part 1 and Part 2 and the difference in the (follow-up – baseline) and (follow-up – fitting) values between Part 1 and Part 2 for all clinical measures except density of white blood cells.
4. For Part 1 and 2: at 14 hours, symptomatic subjects will have a statistically significantly, greater change from baseline in all the clinical measures except density of white blood cells in the eyelid margins.

Other exploratory analyses may be conducted at the discretion of the study responsible clinician.

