The analysis procedure will follow the exact steps for analyzing the change from baseline in mean as described in the primary analysis section for LMS, NIBUT, TMH, and TOSM except the response variable will be the change of LMS, NIBUT, TMH, and TOSM from the corresponding baseline and the covariate baseline LMS, NIBUT, TMH, and TOSM will be excluded from the model. Comparisons between subject strata will be carried out using a one-sided 95% CI of least-square means differences (symptomatic - asymptomatic) for the change from baseline for the hypothesis given below:

$$H_0: \mu_S - \mu_A \leq 0$$
$$H_A: \mu_S - \mu_A > 0,$$

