### **14.10. Procedure for Reporting Deviations from Statistical Plan**

The analysis will be conducted according to that specified in above sections. There are no known reasons for which it is planned to deviate from these analysis methods. If for any reason a change is made, the change will be documented in the study report along with a justification for the change.

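### Return to pre-lens comfort is tested with a regression intercept that equals the mean change in VAS only if the slope on pre-lens VAS is 1

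*Combined protocol and SAP*

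**What the plan says.** Section 2.3 states the hypothesis as a comparison of two scores in the same subjects: "The measured end of day discomfort score, following lens removal, will not be statistically significantly different than the pre-lens wear discomfort score". Section 14.7, under Part 1 and 2, item 1, gives the analysis. Post-removal VAS is modelled within each stratum and overall, "using a linear mixed model by adjusting the baseline VAS score (pre-VAS) as covariate", with stratum as a fixed effect, age, gender and race where appropriate, and an unstructured or compound-symmetry covariance between the two eyes. The test is on the constant term: "A two-sided 95% CI for the coefficient of the model intercept will be constructed for the hypothesis given below", with a null value of zero.

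The decision rule follows: "End of day discomfort returned to pre-lens wear comfort will be concluded if the 95% confidence intervals contains 0". An interval wholly below or above zero is read as "lower or higher post VAS score compared to pre-VAS score, respectively". The section specifies no centring of pre-lens VAS, no offset, no slope fixed at 1 and no change score as response. Section 14.10 adds: "The analysis will be conducted according to that specified in above sections".

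**The concern.** The hypothesis concerns the mean of post minus pre. The intercept of a regression of post on pre is a different quantity: the predicted post-removal score of an eye whose pre-lens score is 0, in the reference stratum, with any other uncentred covariate (age, for example) also at 0. On the 0–100 scale of section 2.2, where 100 is comfortable, that point lies far from where most subjects are likely to be.

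The rule can therefore declare a difference when comfort has simply returned, and can conclude return, or even improvement, when comfort has fallen. It is applied in both Parts, in each stratum and overall, which makes six conclusions (2 Parts × 3 fits).

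**Working it through.** The plan states no error rate or power for this hypothesis, so there is no figure of its own to reproduce.

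**Inputs from the documents.** Response, covariate, tested parameter and decision rule: section 14.7, item 1. VAS range 0–100: section 2.2. Sample size 27 per stratum, 54 in total: section 14.2.

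**Assumed, because the documents do not give them.** Pre-lens mean 75, SD 15, equal SDs before and after (so the slope is about the pre-post correlation), scores clipped to 0–100, between-eye correlation 0.6 or 0.9.

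**Step 1, identity.** In post = a + b × pre + error,

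a = mean(post) − b × mean(pre) = mean change + (1 − b) × mean(pre).

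So a equals the mean change only if b = 1 or mean(pre) = 0. With stratum in the model, this holds for the reference stratum only.

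**Step 2, size of the bias, (1 − b) × mean(pre).**

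| Mean pre-lens VAS | b = 0.5 | b = 0.7 | b = 0.9 | b = 1 |
|---|---|---|---|---|
| 75 | +37.5 | +22.5 | +7.5 | 0 |
| 80 | +40 | +24 | +8 | 0 |

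At a mean of 70 the bias is +35 (b = 0.5) and +21 (b = 0.7); at 90 it is +45 and +27. Simulated mean intercepts at mean 75 with no true change were about +38, +23 and +8.

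**Step 3, no true change.** Percentage of simulated trials declaring a difference, essentially all as higher post VAS. The two-eye model is compound symmetry fitted by REML, 2,000 trials per cell; the one-pair model is least squares, 4,000 trials per cell.

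| Correlation | Two eyes, n=27 | Two eyes, n=54 | One pair, n=27 | One pair, n=54 |
|---|---|---|---|---|
| 0.5 | 97–98 | 100 | 77 | 98 |
| 0.7 | 82 | 98 | 51 | 85 |
| 0.9 | 35–37 | 60–62 | 19 | 35 |

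A test of the mean change rejected in 4–6%, against a nominal 5%.

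**Step 4, true fall of 10 points (75 to 65), two-eye model.** The expected intercept is −10 plus the bias: +27.5, +12.5 and −2.5 at b = 0.5, 0.7 and 0.9.

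- Correlation 0.5: higher declared in 76–79% (n=27) and 96–97% (n=54).
- Correlation 0.7: lower never declared; higher in 29–30% and 50–51%; return concluded in the rest.
- Correlation 0.9: lower declared in only 11–14% and 17–21%.

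The mean-change test detected the fall in 91–100% of trials across these settings.

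**Step 5, exact cancellation.** At mean 80 and b = 0.7, a true fall of (1 − 0.7) × 80 = 24 points gives an expected intercept of 0. In one-pair runs at n=54, return was then concluded in about 95%.

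**Step 6, would centring help?** No. With pre-lens VAS centred, the intercept becomes the mean post-removal VAS, and testing that against 0 rejected in 100% of simulated runs.

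**The case against.** The strongest objection is that the direction and size depend on unknown spreads. The slope is correlation × SD(post)/SD(pre). If scores spread out after 14 hours of wear, the slope can reach or pass 1. With correlation 0.7 and SDs of 12 before and 18 after, it is 0.7 × 18/12 = 1.05. With mean 75, no true change and one pair per subject, higher was then declared in 2–3% and lower in 1–2%, which is near nominal. With SDs of 10 and 18 the slope is 1.26 and the bias reverses: lower was declared in 9% (n=27) and 16% (n=54). This stands, and it means the false-positive rates above are illustrative. It does not rescue the rule. With SDs of 12 and 18, the rule detected a true 10-point fall in about 22% of trials at n=54, against 100% for the mean-change test.

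Section 14.1 calls the methods general and promises a stand-alone SAP, and section 14.10 allows documented changes. That SAP is not among the documents. However, section 14.7 already fixes the parameter, the null and the decision rule, so an SAP that only adds detail inherits the error.

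Centring is simply not mentioned, so an uncentred covariate is the plain reading rather than an explicit statement. Step 6 shows that the other reading fails too.

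Finally, this is one of the Other hypotheses. If the descriptive summaries of section 14.1 cover pre- and post-VAS, a reversed direction could be seen beside the test. That limits the harm, but the formal conclusion would still be wrong.

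**Conclusion.** The rule is wrong as written. The algebra is exact: with mean pre-lens VAS above 0, the tested intercept is the mean change only when the slope is 1, and any slope below 1 shifts it upward. How far it misleads depends on VAS means, SDs and correlations that the documents do not supply. Under equal SDs and correlations of 0.5 to 0.9, it can exceed the nominal 5% many times over and can report the opposite of a real fall.

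The consequence is confined to this Other objective, in both Parts. It should be fixed, but it does not threaten the primary or secondary analyses.

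**What to change.** Rewrite the paragraph for item 1 of section 14.7:

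- Use post-removal minus pre-lens VAS, per eye, as the response and drop pre-lens VAS as a covariate. Item 4 of the same section already takes change as response, "and the covariate baseline LMS, NIBUT, TMH, and TOSM will be excluded from the model". It is a precedent for the response only, since item 4 compares strata rather than testing a mean change against zero.
- Keep the unstructured or compound-symmetry covariance between eyes, keep stratum as a fixed effect in the overall model, and centre any other covariates.
- Test mean change = 0 with a two-sided 95% CI in each stratum and overall. Define the overall parameter as a least-squares mean change across the two strata with its weighting stated, because under reference coding the intercept is one stratum's mean. Read direction from that interval.
- As a separate wording point, when the interval covers zero, report that no difference was shown and give the interval, since a wide interval is not evidence of return. If a positive claim of return is wanted, the sponsor should set an equivalence margin in advance.

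The cost is one paragraph before database lock. No new data are needed: pre-lens and post-removal VAS are already recorded for each eye at steps 3.2 and 4.12 in Part 1 and steps 7.2 and 8.12 in Part 2.

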### **14.2. Sample Size Justification**

The sample size was not determined by any empirical power calculation. The plan is to enroll approximately 210-240 subjects with a completion target of 27 subjects per strata (Symptomatic and Asymptomatic). Assuming a sample of size 27 subjects per strata, the statistical power was calculated using SAS procedure PROC POWER. The goal is to show Symptomatic subjects have, on average, lower Non-invasive tear Breaks up Time (NIBUT) and Tear Meniscus Height (TMH); and greater Lid Margin Staining (LMS), Tear Film Osmolarity (OSM), and White Blood Cell (WBC) count compared to Asymptomatic subjects.

Table 4 contains the information of two previous studies and their corresponding subject disposition. Tables 5 to Table 9 below summarizes the primary endpoints from the studies [REDACTED] and [REDACTED] that are corresponded to the current study and therefore used to compute the power.

Table 4: Historical Studies Included

Study	Study Design	Endpoints Collected	No. of Enrolled	No. of Completed - Asymptomatic	No. of Completed - Symptomatic
[REDACTED]	Cross-sectional study of subjects wearing Dailies AquaComfort Plus	Lid Margin Staining, NIBUT, TMH, Tear film osmolarity,	42	25	16
[REDACTED]	Cross-sectional study of subjects	Lid Margin Staining,	74	27	15

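### Section 14.7 takes a 95% interval that contains 0 as proof that comfort has returned to its pre-lens level, so imprecise data favour the claim; the main risk is that a modest loss is missed within a stratum of 27

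*Combined protocol and SAP*

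**What the plan says.** Section 2.3 (Other Hypotheses, For Part 1 and 2, item 1) words the claim itself as non-significance: "The measured end of day discomfort score, following lens removal, will not be statistically significantly different than the pre-lens wear discomfort score".

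Section 14.7 (For Part 1 and 2, item 1) gives the analysis and the decision rule:

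- Model: "Within each stratum and overall post VAS score for both eyes will be analyzed separately using a linear mixed model". The pre-lens score enters this model on the right-hand side: "by adjusting the baseline VAS score (pre-VAS) as covariate".
- Test: "A two-sided 95% CI for the coefficient of the model intercept will be constructed for the hypothesis given below", the null hypothesis being that the intercept is zero.
- Decision: "End of day discomfort returned to pre-lens wear comfort will be concluded if the 95% confidence intervals contains 0". The only alternative is: "Otherwise, statistical difference between end of day comfort and pre-lens comfort will be concluded". The sign of the interval then gives the direction.

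The two scores are the VAS comfort before lens application and after lens removal on the single study day (steps 3.2 and 4.12 in Part 1, 7.2 and 8.12 in Part 2). Section 14.2 sets a target of 27 completers per stratum and says: "The sample size was not determined by any empirical power calculation". Its power tables (Tables 10 to 14) cover the five clinical measures and not VAS comfort. No equivalence margin for comfort and no minimum precision appears anywhere in the document.

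**The concern.** An interval that contains 0 can mean that the change is close to zero, or that the data are too imprecise to tell. The rule gives both cases the same affirmative answer. The incentive therefore runs backwards: fewer completers, noisier scores and more missing values all widen the interval and make a claim of return more likely. Section 14.9 does not impute missing values in the main analysis, so lost data push the same way. The rule is also applied within each stratum, where precision is lowest.

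At stake is a stated objective (section 2.1, Other Objectives, item 2), examined in both Parts. The report could say that comfort recovers after lens removal when the data only failed to show that it did not.

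**Working it through.** **No figure to reproduce.** The plan gives no power, SD or margin for this question. As a check on the sample size, a one-sided 5% two-sample t-test with 27 per stratum reproduces the plan's own tables (for example lid margin staining, difference 0.35 and SD 0.5: 81.4% against the stated 81%). So 27 and 54 are the right numbers to use here.

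**Which contrast.** With pre-lens VAS as a covariate, the intercept is the expected post-removal score at a pre-lens score of 0 (for the reference stratum in the overall model). It is not the mean change. The check below assumes that this has been corrected to the mean post-minus-pre difference, to see whether the decision rule is sound in itself.

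**Inputs.**
- n = 27 (one stratum) and n = 54 (overall), from section 14.2; eyes averaged within subject.
- Two-sided 95% interval, from section 14.7.
- VAS from 0 to 100, from section 2.2.
- SD of the post-minus-pre change: 10, 15 or 20 points. This is assumed.

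**Formulas.** SE = SD/√n. Half-width = t(0.975, n−1) × SE. For a true loss d, the chance that the interval contains 0 is P(|T| < t(0.975, n−1)), where T is noncentral t with n−1 degrees of freedom and noncentrality d/SE. The critical values are 2.056 (n = 27) and 2.006 (n = 54).

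| n | SD | SE | Half-width | d/SE for a 5-point loss | Declared returned, true loss 5 | Declared returned, true loss 10 |
|---|---|---|---|---|---|---|
| 27 | 10 | 1.92 | 4.0 | 2.60 | 29% | 0.1% |
| 27 | 15 | 2.89 | 5.9 | 1.73 | 61% | 8.5% |
| 27 | 20 | 3.85 | 7.9 | 1.30 | 76% | 29% |
| 54 | 10 | 1.36 | 2.7 | 3.67 | 5% | 0% |
| 54 | 15 | 2.04 | 4.1 | 2.45 | 33% | 0.2% |
| 54 | 20 | 2.72 | 5.5 | 1.84 | 56% | 5% |

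In every column the chance of declaring return rises with the SD and falls with n. A sound rule for claiming sameness would do the opposite.

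**The same question under an equivalence rule.** Suppose return is claimed only if a 90% interval lies inside ± a margin (two one-sided tests at 5%). The margins of 5 and 10 points are illustrations only, since the documents give none. A true loss equal to the margin is then declared returned at most about 5% of the time at any of these SDs. The chance of claiming return when nothing has changed is, for SD 10, 15 and 20:
- margin 10: 99.9%, 91.6%, 62.3% (n = 27); 100%, 99.9%, 95.3% (n = 54);
- margin 5: 62.5%, 9.2%, 0.3% (n = 27); 95.2%, 55.9%, 14.4% (n = 54).

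Noise now lowers the chance of the claim.

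**The case against.** **The percentages are not the error rates of the rule as written.** This stands. The plan tests an intercept, and that test behaves differently. In a simulation with 27 subjects, an assumed pre-lens mean of 85 with SD 10 and residual SD of 10 to 15, a true 10-point loss was declared returned 91–93% of the time when the slope of post on pre was 1. With slope 0.5 it was declared returned 54–77% of the time and declared higher comfort 23–46% of the time; with no change at all, higher comfort was declared 36–66% of the time. So a reader who infers that the written rule answers yes by default goes too far: under some slopes it gives a wrong direction instead. The intercept is a separate defect, and arguably the larger one. Correcting it does not cure the decision rule.

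**A reader might infer that a clear loss of comfort would often be declared recovered.** The documents do not support that. They give no SD for VAS change and do not say what size of loss matters. For a 10-point loss the chance is at most 8.5% at n = 27 and 0.2% at n = 54 when the SD is 15 or less. The overall analysis, which the plan also requires, would usually detect such a loss.

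**The interval is constructed anyway, and section 2.3 speaks only of non-significance.** A reader given the interval could judge its precision. That softens the harm, but section 14.7 goes beyond non-significance and fixes an affirmative conclusion of return.

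**The objective ranks low.** True: it is outside the primary and secondary hypotheses governed by section 14.4.

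**Conclusion.** The rule is wrong as written: non-significance is taken as evidence of return, with no margin and no inconclusive outcome, and nothing elsewhere in the document repairs this. That conclusion needs no assumption about the SD. The size does. It applies to the corrected mean-difference contrast, with an assumed SD of change of 10 to 20 points. On that basis the risk lies mainly in modest losses within a stratum: 29–76% for a true 5-point loss at n = 27, against 5–56% at n = 54. For a 10-point loss it is material only towards an SD of 20 within a stratum (29%). The sponsor should change the rule, but the five primary comparisons are unaffected.

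**What to change.** In section 14.7, and in the SAP that section 14.1 says will be finalised before database lock:

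1. Replace the intercept test by the mean post-removal minus pre-lens VAS difference with its confidence interval, within each stratum and overall, in each Part.
2. Conclude that comfort returned only if the interval lies wholly inside an equivalence margin that the sponsor fixes and justifies before database lock. A 90% interval corresponds to two one-sided tests at 5%; a 95% interval is a stricter choice.
3. Otherwise, or if no margin is set, report the interval and state only that a difference was or was not detected.
4. Reword the hypothesis in section 2.3 to match.

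The cost is a change of wording and one clinical decision on the margin; no extra subjects, visits or measurements are needed. The downside is real: with a tight margin the claim may be hard, or nearly impossible, to support within a stratum of 27, as the illustrative 5-point margin shows. Step 3 needs no margin and still gives an honest report.
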